7.0. Treatment Protocol

7.1 Study Outline

Patients who receive HMA and other outpatient chemotherapy typically have declines in their blood counts during the 1st month of therapy before improvements are noted. Therefore, we will initiate our intervention at cycle 2 the earliest. HMA and other common chemotherapy are administered daily as an infusion or subcutaneous injection for 5-10 days every 4 weeks. There are outpatient chemotherapy that are pill-based as well (e.g., enasidenib, ivosidenib) and are also dosed every 4 weeks. We will consent patients and they will complete measures during routine visits. They will complete baseline measures during the 4th week of a chemotherapy cycle up to day 1 of the subsequent cycle prior to chemotherapy administration (study week 0) (Figure 1). The intervention will start during the 1st week of of a new cycle (study week 1) and will last 8 ± 4 weeks. The post-intervention measures will be completed 2 cycles later during the 4th week of the cycle (study week 8 ± 4). To illustrate this, if the intervention starts in cycle 2 week 1, baseline measures will take place on cycle 1 week 4, and postintervention assessment will place on cycle 3 week 4. If the intervention starts in cycle 6 week 1, baseline measures will take place on cycle 5 week 4, and post-intervention assessment will place on cycle 7 week 4.

At the screening visit, we will confirm if the patient is eligible using the eligibility criteria above. Once we confirm their eligibility, we will obtain either in-person or verbal consent. The patient will then complete a demographic questionnaire that asks about the participant's age, gender, race, ethnicity, education level, marital status, employment status, and Eastern Cooperative Oncology Group (ECOG) performance status as well as their cancer and treatment characteristics (see Section 7.2).

For Aim 1, one interview will be conducted with each participant in a private space for approximately 30 minutes. First, we will explain the rationale and demonstrate the use of the GO-EXCAP Mobile App. Second, we will elicit preferences for the content, format, and delivery of the intervention (Table 2). Collectively, the findings will be used to adapt the intervention.

Feature	Goal	Example of Adaptation
Content	To confirm the frequency, intensity, and duration of the exercises and appropriate percentage increment of steps and resistance band training exercise.	If patients report that they are less able to exercise on the days of chemotherapy, we will plan to maintain rather than increase the number of steps and intensity of resistance training exercises during those days.
Format	To elicit preferences regarding the format of the training manual	If patients prefer an electronic training manual, we will develop this and incorporate it into the mobile app.

Table 2: Intervention features and example of adaptation based on feedback from natients

	(i.e. paper, audio, video, or a combination).	
Delivery	To elicit preferences in the administration of the intervention (i.e. in-person, through the app, or a combination of both).	If patients prefer the intervention to be administered entirely through the app (without the baseline visit with an exercise physiologist), we will develop a video to demonstrate the exercise techniques on the mobile app.

For Aim 2: Participants will be provided with an activity tracker to measure daily steps over 4-7 days. After baseline measures (including blood samples), participants will meet with an exercise physiologist in-person and/or via zoom/phone who will demonstrate how to perform the exercises and the basic features of the mobile app. Both the assessments and teaching will be conducted either at [name] Exercise, Activity and Kinesiology (PEAK) laboratory and/or virtually via zoom/phone. Alternatively, if requested, certain assessments and teaching will be completed at the cancer center. Patients will be provided with the GO-EXCAP Mobile App on a tablet which will be equipped with cellular connectivity. The Exercise Physiologist and/or study coordinator will ensure successful set up of tablet device for the subjects and he/she will also provide in-person instructions on the use of the mobile app. The study coordinator will also be available to answer any potential subsequent questions in regards to the use of the app.

For Wilmot affiliated sites (except for Olean, Dansville, and Wellsville where research activities will not be conducted), similar procedures will be used if participants are willing to travel to Wilmot Cancer Institute/Strong Memorial Hospital. For participants who are not willing to travel, our study coordinator will perform assessments at the affiliated sites. Blood samples will also be collected. Teaching will be conducted either in-person or via zoom. Assessments that are required to be performed at the PEAK lab will be omitted if participants are not willing to travel.

From study week 1-8 (\pm 4), participants will perform the exercises at home. Participants will enter their daily steps from the activity tracker, time spent for resistance band exercises, and exercise intensity into the mobile app. They will enter any barriers to exercise on the app and complete the PRO-CTCAE questionnaire weekly. These data will be transferred automatically from the app to a Web portal. The study team (physiologist) will log into the Web portal twice a week to monitor adherence, provide feedback, and adjust exercise prescriptions. These recommendations will be available to each participant via the app or directly. Participants can interact with the physiologist via the app or directly. The study coordinator will also call the patients weekly to answer any questions. The algorithms for symptom reporting and management developed in Aim 1 will be incorporated into the app. To ensure safety, participants will answer questions weekly on the app to determine ongoing appropriateness of exercise (e.g., no interval cardiac symptoms) and ensure there are no new medical contraindications to exercise.⁹⁵

Mid-intervention (study week 3-5): We will conduct an in-person or zoom/phone interview (approximately 30 min) with participants. A three-week window will be used to conduct interviews with participants. App functionality, usability, and barriers to adherence will be elicited.

Post intervention (study week 8 ± 4 weeks; chemotherapy delay is common due to cytopenias): We will collect the same measures as baseline (including blood samples) and usability data. An exit interview (approximately 30-45 min) will be conducted with participants either in-person or via zoom/phone to elicit app functionality, usability, and barriers to adherence. Participants who complete both the baseline and post-intervention measures will receive \$50. They may keep the exercise kit and activity tracker (value \$150).

Procedures at the affiliated sites will follow the baseline assessments.

7.2. Baseline Assessment of the Participants

Demographics, clinical and treatment/cancer characteristics will be collected.

7.2.1. Socio-Demographics and Clinical Characteristics

Patient's age, race, ethnicity, gender, highest level of education achieved, employment status, marital status, and ECOG performance status will be captured from the patients. The socio-demographics and clinical characteristics will only be collected at baseline.

7.2.2. Cancer and Treatment Characteristics

Type of myeloid neoplasms, prior hematologic malignancies, cytogenetic risk group and treatment regimen will be abstracted from the medical records. This information will be collected at baseline only.

7.2.3. Outcomes of Interest (Baseline and post-intervention unless otherwise specified)

For patient-reported questionnaires, if we are unable to provide assessment forms to the participants, these will be mailed to them at least 1 week ahead of time. For assessments that needed to be conducted in-person (including blood sample collection), these may be omitted when appropriate for safety of the patients.

7.2.3.1. Physical Function

Short Physical Performance Battery (SPPB): The SPPB is an objective physical assessment evaluating lower extremity physical function.⁹⁶ It is comprised of a four-meter walk, repeated chair stands and a balance test. Impairment on SPPB testing has been shown to be predictive of short-term

mortality and nursing home admission in community-dwelling older adults. We will also perform the virtual SPPB via the phone/zoom, which evaluates the participants' perceived ability to perform above tests (walking, repeated chair stands, and balance).

7.2.3.2. Fatigue

Brief Fatigue Inventory (BFI): BFI is a 9-item, patient-report instrument with established reliability and validity that we have used in previous studies.⁹⁷ The BFI allows for the rapid assessment of fatigue level in cancer patients and identifies those patients with severe fatigue. The reliability and validity of the BFI were demonstrated in a study of 305 cancer patients and 290 community-dwelling adults.⁹⁸

7.2.3.3. Depression

Center for Epidemiological Studies Depression Scale (CES-D): The CES-D is a 20-item depression scale developed and validated for use with a variety of populations.⁹⁹ It is in a format similar to that of the Beck Depression Inventory, but with less emphasis on physical symptoms of depression that may be confounded with disease symptoms or treatment side effects. It has been shown to reliably and validly measure depression in cancer populations.¹⁰⁰

7.2.3.4. Quality of Life (QOL)

Functional Assessment of Cancer Therapy-Leukemia (FACT-Leu): The FACT-Leu scale was created by combining the Functional Assessment of Cancer Therapy-General module (FACT-G) and a sub-scale made up of 17 leukemia-specific items.¹⁰¹ It been tested and determined to be a valid, reliable, and efficient instrument for evaluating leukemia-specific healthrelated QoL.

7.2.3.5. Self-efficacy for Exercise and Exercise Adherence

Self-Efficacy for Exercise scale: This is a 9-item scale to measure self-efficacy for exercise and higher score indicates higher self-efficacy.¹⁰²

Actigraphy (research-grade). The actigraph is a small, lightweight, noninvasive device worn on the waist (clipped to clothes or worn as a waistband). The actigraph contains an accelerometer that quantifies duration and intensity of physical activity and sedentary behavior throughout the day and week. We will use an actigraph that provides calculated energy expenditure values for active energy expenditure in kilocalories and total energy expenditure in metabolic equivalents per time in kilocalories/min/kg. We will use software supplied by the manufacturer

Protocol Version: 22OCTOBER2021

to determine bouts of moderate or higher activity during each assessment period (T1, T2, and T3). This is a research-grade device that complements the commercial-grade wrist-worn Garmin activity tracker.

Exercise Readiness: This will be assessed using the Physical Activity Readiness Questionnaire (PAR-Q+) form. This is designed to assess patients' readiness to participate in more physical activity or engage in a fitness appraisal.

7.2.3.6. Other Geriatric Assessment Measures

Activities of daily living (ADL): ADLs are measures of self-care. ADL independence will be assessed using the Katz Index of Independence in Activities of Daily Living, commonly referred to as the Katz ADL. The Katz ADL is the most appropriate instrument to assess functional status as a measurement of the client's ability to perform activities of daily living independently. Clinicians typically use the tool to detect problems in performing activities of daily living and to plan care accordingly. The Index ranks adequacy of performance in the six functions of *bathing*, *dressing*, *toileting*, *transferring*, *continence*, *and feeding*. Clients are scored yes/no for independence in each of the six functions. A score of 6 indicates full function, 4 indicates moderate impairment, and 2 or less indicates severe functional impairment.

Instrumental Activities of Daily Living (IADL): Self-reported functional status will be assessed using the IADL subscale of the Multidimensional Functional Assessment Questionnaire: Older American Resources and Services (OARS). The IADL subscale consists of seven questions rated on a three-point Likert scale. It measures the degree to which an activity can be performed independently.

Fall History: A self-reported history of falls in the past three months will be recorded. A history of a recent fall has been demonstrated to be independently predictive of increased risk for chemotherapy toxicity in older cancer patients.²⁰

6-minute walk test (6MWT): The 6MWT measures functional endurance and aerobic capacity.¹⁰³ It measures the distance walked by the patient over a time of 6 minutes. We will also assess gait analyses using the BTS G-SENSOR. The BTS G-SENSOR is a small non-invasive device worn on a waist belt to provide functional evaluation of walking that includes accelerometers, gyroscopes, and magnetometers, allowing the spatiotemporal parameters of subject's gait to be measured as well as their pelvic rotations and swing leg accelerations. It provides objective and quantitative data that is related to muscles activity and kinematic parameters.

Protocol Version: 22OCTOBER2021 Page

Nutrition: Screening for nutritional deficit will be performed with body mass index (BMI) evaluation and self-reported weight loss.

Cognition; Montreal Cognitive Assessment (MOCA): A 30-point cognitive screen test with excellent sensitivity for individuals with mild dementia and mild cognitive impairment. It can also be used to trend changes in cognitive status over time. If in-person assessment is not possible, MOCA-blind will be conducted via zoom/phone.

Comorbidity (baseline only); OARS Physical Health Section: Patients selfreport their coexisting medical conditions and also rate the degree to which their illness causes impairment in daily activities. The OARS Physical Health Section has been shown to correlate significantly with health professional ratings of comorbidity as well.

Social Support (baseline only); OARS Medical Social Support survey: A 13-question survey asking patients to identify the number of support persons involved in their medical care as well as the degree to which they felt supported in a variety of situations.

Medications (baseline only): We will record all prescription and nonprescription medications, dosage and frequencies from the medical records. Polypharmacy is defined as the use of 5 or more medications.

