The feasibility of the GO-EXCAP Mobile App will be evaluated based on the following: a) Percentage of patients wearing the activity tracker and entering resistance exercise data into the mobile app and b) Percentage of patients performing both walking and resistance exercises during the study period days. Recruitment rates (percentage of patients who are approached and agree to enroll) and retention rates (percentage of patients who are enrolled and complete post-intervention assessments) will also be described

We will consider the intervention feasible if 1) \geq 70% of patients wear the activity tracker and enter resistance exercise data into the mobile app on at least 50% of the study period days, and 2) \geq 70% of patients performed both walking and resistance exercises on at least 50% of the study period days. We chose these criteria based on our previous mobile app study¹⁶ and on published exercise studies in older patients with AML.^{29,30} We will report percentage of adherence with 95% exact confidence interval (CI) calculated by the Clopper-Pearson method. We anticipate that about 20-30% of the participants will withdraw before post-intervention assessment due to rapid disease progression or death. These patients will not be included in the feasibility analysis because their withdrawals from the study are not related to the intervention. With 25 patients enrolled we anticipate at least 17 patients to be evaluable for our feasibility aims. When we estimate the percentage of adherence, a 95% CI will span approximately +/- 25%. For example, if we observe 12/17 (71%) patients complete the tasks, the CI will be 44-90%.

We will also tabulate the recruitment rates, retention rates, and intervention usability, and collect the reasons patient decline to be enrolled. In addition, we will evaluate the distribution and describe the following measures using descriptive statistics: 1) activity levels, 2) physical function (SPPB/vSPPB), 3) fatigue (BFI), 4) depression (CES-D Scale), 5) quality of life (FACT-Leu), and 6) Other geriatric assessment measures. Differences in activity levels, physical function, fatigue, depression, quality of life, and other geriatric assessment measures between pre- and post-treatment will be assessed using paired t-tests or Wilcoxon signed rank tests. Anticipated sample size of more than 12 patients with baseline and follow-up data will be sufficient to obtain the preliminary estimates of the outcomes measures.^{115,116}

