9.0. DATA MANAGEMENT

9.1. Data Collection Table (Aim 2)

	SCHEDULE OF DATA COLLECTION			
	Eligibility and Consent Form	Baseline Assessment (week 0)	Mid- Intervention Assessment (week 3-5)	Post- intervention Assessment* (week 8± 4)
Written Informed Consent	X			
Demographics		X		
Cancer and Treatment Characteristics		X		
Qualitative Interview			Х	Х
Activity Levels (Activity Tracker)		Х		х
Exercise Habits and Readiness		Х		
Short Physical Performance Battery ^b /Virtual Short Physical Performance Battery		Х		Х
Brief Fatigue Inventory (BFI)		X		Х
Center for Epidemiologic Studies Depression Scale (CES-D)		Х		Х
Functional Assessment of Cancer Therapy-Leukemia (FACT-Leu)		Х		Х
Self-Efficacy for Exercise		X		Х
Actigraphy ^{b,d}		X		Х
Geriatric Assessment Measures • Activities of Daily Living		х		Х

 Instrumental Activities of Daily Living Fall History 6-Minute Walk Test^{b,d} Montreal Cognitive Assessment (MoCA or MOCA Blind) 		
Bioelectrical Impedance System ^{a.b,d}	X	Х
Handgrip Dynamometer ^{b,d}	X	Х
Muscle Strength Testing ^{a.b,d}	X	X
Heart Rate Variability ^{a,b,d}	X	X
Feasibility metrics		X
System Usability Scale		X
Complete blood count (from electronic medical record)	X	X
Blood samples ^b	X	X

^aIf patient elects to undergo the assessments at the cancer center instead of the Physical Exercise, Activity and Kinesiology laboratory, these assessments will not be conducted.

^bMay be omitted for patient safety (i.e., if in-person assessments are not possible)

dIf research activities are conducted at Wilmot affiliated sites, these assessments may be omitted

9.2. All hardcopy research records will be stored onsite in the URMC, in locked research files at the James P. Wilmot Cancer Center. The Cancer Center is secured with electronic key cards. Offices within the Cancer Center are again secured by key and data is kept in locked file cabinets. Electronic research records are stored on the URMC's password secured and firewall protected networks. These are the same methods of security used for patient medical records. All study data (including the electronic data kept by the PointClick Care company) will be kept for a period of 7 years after the study and all reports and publications are complete.

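### Fall history uses the same three-month recall at visits about 8 weeks apart, so at week 8 about 38% of the second window predates the intervention and the pre-post comparison of falls is diluted.

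*Combined protocol and SAP*

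**What the plan says.** Section 7.2.3.6 defines the item: "Fall History: A self-reported history of falls in the past three months will be recorded". The only reason given for it is prognostic: "A history of a recent fall has been demonstrated to be independently predictive of increased risk for chemotherapy toxicity".

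Four places fix when it is collected.

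- The parent heading sets the default timing: "7.2.3. Outcomes of Interest (Baseline and post-intervention unless otherwise specified").
- Items meant for baseline alone carry a label, for example "Comorbidity (baseline only); OARS Physical Health Section". Social support and medications are labelled the same way. Fall history is not.
- The schedule in section 9.1 lists it in the geriatric assessment row ("Instrumental Activities of Daily Living Fall History"), which is marked at week 0 and at week 8 ± 4.
- For the post-intervention visit, section 7.1 says: "We will collect the same measures as baseline (including blood samples) and usability data".

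On spacing, section 7.1 says: "The post-intervention measures will be completed 2 cycles later during the 4th week of the cycle (study week 8 ± 4").

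On analysis, section 8.2.2 says that differences in "other geriatric assessment measures between pre- and post-treatment will be assessed using paired t-tests or Wilcoxon signed rank tests". Falls come in through that group name only. No section shortens the recall at the second visit, asks for falls since baseline, or says whether a count or a yes/no answer is recorded.

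**The concern.** The recall period is longer than the planned gap between the visits. A patient who fell two weeks before baseline and never fell on study would, answering correctly at week 8, report a fall at both visits. The paired comparison would show no change for that patient, although the fall belongs to the period before exercise began.

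Part of the second measurement therefore repeats the first, which pulls the pre-post difference toward zero. A fall in the rate and a rise in the rate are both understated. The size of the pull varies between patients because the visit may take place anywhere from week 4 to week 12. Since no fall dates are specified, the data cannot be separated after collection for patients who already reported a fall at baseline.

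**Working it through.** The documents give no fall rate, effect size or power for falls, so there is no planned figure to reproduce.

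**Inputs**

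- Recall length L: three months (section 7.2.3.6), taken as 13 weeks, or 12 weeks if a month is read as four.
- Time t from intervention start to the post-intervention visit: nominally 8 weeks, range 4 to 12 (section 7.1).
- Evaluable patients: at least 17 expected (section 8.2.2).
- Fall risk: not given. 20% of patients per three months is assumed below for illustration.

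**Step 1. Share of the second window that predates the intervention** = max(0, L − t)/L.

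| Visit | L = 13 weeks | L = 12 weeks |
|---|---|---|
| Week 4 | 9/13 = 69% | 8/12 = 67% |
| Week 8 | 5/13 = 38% | 4/12 = 33% |
| Week 12 | 1/13 = 8% | 0/12 = 0% |

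These shares need no fall rate.

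**Step 2. Effect on counts.** Let the weekly fall rate be a before the intervention and b during it, each constant. The expected baseline count is aL, and the expected second count is a(L − t) + bt. The observed difference is (b − a)t, against a true difference over an equal window of (b − a)L. The fraction kept is t/L. With L = 13 this is 4/13 = 31% at week 4, 8/13 = 62% at week 8 and 12/13 = 92% at week 12.

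At week 8, elimination of falls (b = 0) shows as a 62% reduction, and a doubling shows as (5 + 16)/13 = 1.62, a 62% rise. A true halving shows as a ratio of (5 + 4)/13 = 0.69 instead of 0.50.

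**Step 3. Effect on a yes/no measure, week 8, L = 13, assuming 20% fall per 13 weeks and a constant-rate model.**

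- Elimination: 1 − 0.8^(5/13) = 8.2% report a fall, against 20% at baseline. The reduction is (20 − 8.2)/20 = 59%.
- Doubled rate: 1 − 0.8^(21/13) = 30.3%. The rise is (30.3 − 20)/20 = 51%.

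**Step 4. How many patients, with an unchanged rate.**

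- On-study fallers by week 8: 1 − 0.8^(8/13) = 12.8%.
- Reporting a fall at week 8 with only earlier falls: 20 − 12.8 = 7.2% of patients, which is 7.2/20 = 36% of those reporting a fall. The 36% becomes 34-37% for an assumed three-month risk of 30% to 10%.
- Of 17 patients: 17 × 0.20 = 3.4 report a fall, 17 × 0.128 = 2.2 fell on study, and about 1.2 did not.

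**The case against.** The strongest reply is that little rests on this item. Falls appear in no hypothesis, feasibility metric, feasibility threshold or sample-size statement. Section 8.2.2 seeks preliminary estimates, and the stated rationale for the question is prognostic. The study is single-arm in patients on continuing chemotherapy, so a change in falls could not be attributed to exercise in any case. With two or three on-study fallers expected under the 20% assumption, no paired test is informative under either wording. All of this stands and limits the weight of the point. It does not justify counting pre-intervention falls in a post-intervention figure.

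Four stronger readings are tempting but go beyond the documents.

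- *Every second window overlaps the first.* This fails near week 12. The overlap is zero on a 12-week reading. Section 7.1 also allows baseline measures up to about a week before the intervention starts, so a week-12 visit can come about 13 weeks after baseline.
- *The typical overlap is about two thirds.* That is the week-4 edge. Two four-week cycles put the visit near week 8, and the only reason section 7.1 gives for the tolerance is chemotherapy delay, which moves visits later.
- *On-study falls can never be identified.* A patient who reports none at baseline and one later can be classed as an on-study faller if recall is accurate. The ambiguity is confined to patients with a fall at baseline.
- *Exercise-related falls would escape safety monitoring.* The item is not described as a safety instrument. Section 7.1 provides weekly safety questions and weekly calls, and section 11 covers adverse events related to the intervention. That reporting does not guarantee that every fall is captured, since Grade 1 events and expected Grade 2 and 3 events need no report. But a gap in safety monitoring does not follow from the recall wording.

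A last reply is that identical wording at both visits keeps recall comparable. This is a real trade-off, taken up under the fix.

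**Conclusion.** The point holds as a minor measurement flaw. At the planned week-8 visit about 38% of the recalled period (33% on a 12-week reading) predates the intervention, and the pre-post comparison of falls is pulled toward no change. The 62% retention at week 8 applies to expected counts and assumes constant rates within each period and accurate recall. On a yes/no measure the figures are about a 59% reduction for elimination and a 51% rise for a doubled rate, and these also rest on the assumed 20% risk. Because the dilution depends on visit timing, a single correction factor would not repair the pooled comparison.

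For a patient who fell before baseline, a positive answer at the second visit cannot be assigned to the study period. Under the 20% assumption this misclassifies about one of 17 patients. The feasibility conclusion and the sample size are untouched.

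**What to change.** 1. Keep the three-month question at baseline, which preserves its prognostic use.
2. At the post-intervention visit, ask for the number of falls since the baseline assessment date, and record the days covered.
3. In section 8.2.2, state that falls will be reported descriptively: the number of on-study fallers, and falls per person-month in each period (baseline falls over 3 months; on-study falls over the actual months since baseline).

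The two periods then no longer overlap, and none of the expected rate difference is lost to re-counting.

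The cost is one questionnaire line and one sentence in section 8.2.2. The drawback is a shorter recall period at the second visit than at baseline. Rates adjust for the difference in exposure time but not for any difference in recall accuracy, which is a further reason to keep the comparison descriptive. Where baseline is completed some days before the intervention starts, the on-study period also includes those days, up to about a week. The change has to be made before the second visits take place, because without fall dates the split cannot be recovered later for baseline fallers.
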